10.3 Analysis Datasets

Intent-to-Treat Analyses: All analyses will be performed on two samples: 1) the intent-to-treat sample consisting of all randomized subjects (n=52) and 2) the Per Protocol sample (individuals that completed all 20 sessions).

10.4 Description of Statistical Methods

10.4.1 General Approach

Prior to formal statistical analysis, summary statistics for all variables will be obtained and graphical displays will be generated (e.g., spaghetti plots, boxplots). All behavioral outcome measures will be based on standardized composite scores from the literature. These analyses will be used to identify potential heterogeneity and imbalance of randomization into the intervention arms within strata.

All baseline characteristics will be evaluated and considered for inclusion as covariates in the supportive and secondary comparative analyses based on baseline differences among treatment groups and clinical importance. We will also use data reduction techniques (such as factor analysis or principle component analysis) to confirm the applicability of the composite scores in our population.

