10.4.2 Analysis of the Primary and Secondary Endpoint(s)

The efficacy of RS-tDCS to effect the outcomes of each Aim 1 & 2 will be tested using linear mixed effects models. The dependent measures (K10 score, NA, percent of days of use, CWS, MCQ-17) will be nested within timepoint (Visit 1, 5, 10, 15, 20), with active/sham as fixed effects. This will be done using the Matlab function 'fitlme' with REML estimation predicting change from V1 values following each 5 session RS-tDCS interval (Matlab, R2020a, The MathWorks Inc.).

Given that the purpose of this pilot study is to develop effect sizes for a subsequent R01, we will also derive least-squares means effect sizes of our research strategy on distress, NA, percentage of days of use in 4 intervals [V1-V5; V6-V10; V11-V15; V16-V20]. The number of days that elapsed in each interval will be used as a covariate.

CONFIDENTIAL

This material is the property of the NYU School of Medicine and Langone Medical Center. Do not disclose or use except as authorized in writing by the study sponsor
Interventional Template Version: 11 January 2019

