10.6 Measures to Minimize Bias

10.6.1 Enrollment/Randomization/Masking Procedures

In this pilot RCT, participants will be randomized 2:1 into one of two intervention groups consisting of active (Group 1) vs. sham (Group 2) tDCS paired with mindfulness meditation practice. A study team member who otherwise will not be involved in administering research procedures will randomize the device and keep the assignments in confidentiality (e.g. password protected spreadsheet).

During a sham session, the device is programmed to ramp up to the desired intensity (2.0 mA) and ramp down for the initial 60 seconds, with no current delivery during the session aside from the 60 seconds in the beginning and then again at the end of the session. These brief periods of stimulation serve to mimic the effects of a true stimulation session.

Randomization: We will stratify randomization by years of cannabis use (4 years or less vs. 5 or more years). Urn randomization will be used to balance the randomization assignment with respect to these strata. The purpose of stratification is to distribute this potential prognostic factor equally across treatment groups.

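### The stratification factor and the baseline outcome value are missing from the planned models, and other covariates are chosen partly on observed imbalance

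*Combined protocol and SAP*

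**What the plan says.** - **Randomisation (section 10.6.1).** "We will stratify randomization by years of cannabis use (4 years or less vs. 5 or more years"). The method is an urn scheme: "Urn randomization will be used to balance the randomization assignment with respect to these strata". The reason given is prognostic: "The purpose of stratification is to distribute this potential prognostic factor equally across treatment groups".
- **Model for both aims (section 10.4.2).** The dependent measures "will be nested within timepoint (Visit 1, 5, 10, 15, 20), with active/sham as fixed effects". The model predicts change from the first-visit value. No stratum term and no baseline term are listed. For the effect-size estimates one covariate is named: "The number of days that elapsed in each interval will be used as a covariate".
- **Hypotheses and supplementary models (section 10.2).** The test is of a treatment-by-time interaction. The supplementary factors are gender, age, PDDS, BDI, STAI and CUDIT-R; years of use is not among them.
- **Covariate rule (section 10.4.1).** All baseline characteristics are to be "considered for inclusion as covariates in the supportive and secondary comparative analyses", and the choice is made "based on baseline differences among treatment groups and clinical importance". The strata are mentioned here only in connection with a descriptive check for imbalance.

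No section commits to putting the stratification factor into a model, and none rules it out.

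**The concern.** A factor judged prognostic enough to stratify on should normally be in the analysis model. Stratifying makes the arms more alike on that factor, so the variance of the arm difference falls. A model without the factor leaves its contribution in the residual and reports a standard error that is too large. The baseline value of the outcome raises a similar issue: a change score fixes the slope on baseline at 1, whereas a baseline term lets the data estimate it.

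The rule in section 10.4.1 adds a second weakness. A difference between randomised arms at baseline is a chance event and does not show that the variable predicts outcome. The rule gives no list and no threshold, and it is applied after the baseline data have been seen. The adjusted secondary results would then depend partly on chance and on judgement after the fact. Section 10.4.2 says that the pilot is meant to supply effect sizes for a later grant, so the precision and reproducibility of those estimates are what is at stake.

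**Working it through.** **The plan's own figure.** Section 10.5 gives an intraclass correlation of 0.8. The design effect is 1 + (5 - 1) × 0.8 = 4.2, and 50 × 4.2 / 5 = 42 participants (28 active, 14 sham). This reproduces. Nothing below changes the 42.

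**Baseline value.** Inputs: outcome variance set to 1 at each visit, and correlation ρ = 0.8 between any two visits. The 0.8 is the plan's figure; using it as the baseline/follow-up correlation is my assumption.

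| | Change score | Adjusted for baseline | Reduction |
|---|---|---|---|
| One visit | 2(1 - ρ) = 0.40 | 1 - ρ² = 0.36 | 1 - 0.36/0.40 = 10% |
| Mean of four visits | 0.85 + 1 - 2ρ = 0.25 | 0.85 - ρ² = 0.21 | 1 - 0.21/0.25 = 16% |

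The variance of the mean of four visits is (1 + 3 × 0.8)/4 = 0.85. These are large-sample values; estimating the slope from 42 participants gives back a little of the gain.

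**Stratum.** Let R² be the share of the variance of change that the stratum explains. The documents give no value, so I take 0, 0.10 and 0.25. With the arms close to balance on the stratum, omitting it inflates the standard error by about 1/√(1 - R²): 1/√0.90 = 1.05 and 1/√0.75 = 1.15.

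A simulation checked this with 42 participants, 2:1 allocation, half in each stratum, a single-endpoint linear model and 6,000 replicates. The plan gives no urn parameters, so a 2:1 urn rule was assumed.

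| R² | SE ratio, omitted / included | One-sided type I error, omitted | One-sided type I error, included | Power at 0.8 SD, omitted | Power at 0.8 SD, included |
|---|---|---|---|---|---|
| 0 | 0.996 | 0.045 | 0.044 | not run | not run |
| 0.10 | 1.05 | 0.043 | 0.050 | 0.78 | 0.81 |
| 0.25 | 1.15 | 0.037 | 0.048 | 0.79 | 0.86 |

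The 0.8 SD effect is an assumption, and power is one-sided at 0.05. Omitting a prognostic stratum makes the test conservative.

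**Imbalance as a selector.** With 28 against 14, the standard error of a standardised baseline difference is √(1/28 + 1/14) = 0.33 SD. Differences of about a third of an SD are therefore ordinary chance, whether or not the variable matters. For the stratifier itself, a Fisher test at p < 0.05 (3,000 replicates under the assumed urn) picked it in under 0.1% of trials. Even so, the arms differed on it by more than 10 percentage points in about 30% of trials and by more than 20 points in about 4%.

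**Interaction.** A stratum main effect adds the same amount at every visit. With complete data it cancels from differences between visits within a participant, and the treatment-by-time interaction is estimated from those differences. Adding the stratum as a main effect therefore leaves the precision of that test unchanged.

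**The case against.** The strongest reply has five parts.

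1. **Clinical importance is also a criterion.** A reader might infer that the rule in section 10.4.1 is bound to pass over the stratifier because randomisation balances it. The documents do not support that. A factor that the plan itself calls potentially prognostic could enter on clinical importance, and an urn balances only in probability. This part stands. What remains is that the second criterion is undefined and leaves the choice open.
2. **The rule does not govern the primary model.** A reader might infer that the imbalance rule is why the main analysis ignores the strata. It is not: the rule covers secondary and supportive comparisons. The main model lacks the stratum because section 10.4.2 does not list it. Removing the rule alone would not put the stratum in. This stands, so the two gaps need separate edits.
3. **Change from the first visit already uses baseline.** True, which is why the further gain is only 10-16%. A stratum effect that merely shifts a participant's level also cancels in the change score, so the stratum must predict change to matter.
4. **The stated hypothesis is an interaction.** This also stands; the benefit lies elsewhere, in arm contrasts and effect sizes.
5. **The rule may select nothing spurious.** A reader might count about 17 baseline measures and compute 1 - 0.95^17 = 58% as the chance that at least one differs at p < 0.05. The plan contains no such test, and many of the measures cover overlapping constructs and will be correlated. That figure should not be used.

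**Conclusion.** The point holds as one of efficiency and pre-specification. The specified models carry neither the stratification factor nor the baseline outcome value, and covariates for other comparisons are chosen partly on observed differences.

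Baseline adjustment lowers the variance of the arm contrast on change by about 10% (one visit) to 16% (mean of four), resting on 0.8 as a common correlation across visits. The stratum's share is purely an assumption: at 10-25% of the variance of change, omitting it costs about 5-15% in standard error; at zero, it makes no material difference. The two gains were worked out separately and should not be added.

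A reader might infer that ignoring the strata threatens the type I error. It does not: omission makes the test conservative. The gain also does not extend to the treatment-by-time test in section 10.2. Because the pilot is intended to produce effect sizes, the change is still worth making.

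**What to change.** - **Section 10.4.2:** pre-specify the years-of-use stratum (4 or less vs 5 or more) and the baseline value of the outcome as fixed effects in the primary and secondary models and in the least-squares-means effect-size estimates.
- **Section 10.4.1:** remove observed baseline differences as a criterion. Replace the rule with a fixed covariate list, and keep baseline tables descriptive.
- **Section 10.2:** bring the supplementary list into line by adding years of use. Gender cannot vary, since section 5.1 admits only women.

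The cost is SAP wording, settled before unblinded data are seen. The stratum is needed to randomise and the baseline values are already collected, so there is no new data collection and the planned 42 is unchanged.

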10.4.2 Analysis of the Primary and Secondary Endpoint(s)

The efficacy of RS-tDCS to effect the outcomes of each Aim 1 & 2 will be tested using linear mixed effects models. The dependent measures (K10 score, NA, percent of days of use, CWS, MCQ-17) will be nested within timepoint (Visit 1, 5, 10, 15, 20), with active/sham as fixed effects. This will be done using the Matlab function 'fitlme' with REML estimation predicting change from V1 values following each 5 session RS-tDCS interval (Matlab, R2020a, The MathWorks Inc.).

Given that the purpose of this pilot study is to develop effect sizes for a subsequent R01, we will also derive least-squares means effect sizes of our research strategy on distress, NA, percentage of days of use in 4 intervals [V1-V5; V6-V10; V11-V15; V16-V20]. The number of days that elapsed in each interval will be used as a covariate.

CONFIDENTIAL

This material is the property of the NYU School of Medicine and Langone Medical Center. Do not disclose or use except as authorized in writing by the study sponsor
Interventional Template Version: 11 January 2019

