Population	N=52 female participants (ages 21-65) with RRMS and CUD
Study Sites	NYU Langone Health [name]
Number of participants	N=52 participants expected to be enrolled at NYU Langone Health
Description of Study Procedure	
tDCS is noninvasive brain stimulation device that modulate brain activity delivering a low-intensity electrical current (2.0 mA) through scalp sponge electrodes. Participants will follow an audio track for guided mindfulness during the stimulation.
 
For Active tDCS, the device is programmed to ramp up to 2.0 mA (for 30 seconds), provide constant current throughout session (19 minutes), and then ramp down (for 30 seconds) at the end.
 
For Sham tDCS the device is programmed to ramp up to 2.0 mA (for 30 seconds) followed by a ramp down (30 seconds), with no current delivery for 18 minutes, and then ramp up (for 30 seconds) and down (for 30 seconds) at the end.

Reference Therapy	

CONFIDENTIAL

This material is the property of the NYU School of Medicine and Langone Medical Center. Do not disclose or use except as authorized in writing by the study sponsor

[figure not shown]
Interventional Template Version: 11 JAN 2019

Key Procedures	Active or sham tDCS with simultaneous mindfulness meditation
Statistical Analysis	Multivariate linear regression will be used to evaluate the outcome of each Aim. The dependent measures will be nested within timepoint (Visit 1, 5, 10, 15, 20), with active/sham as fixed effects.

CONFIDENTIAL

This material is the property of the NYU School of Medicine and Langone Medical Center. Do not disclose or use except as authorized in writing by the study sponsor
Interventional Template Version: 11 January 2019

SCHEMATIC OF STUDY DESIGN

CONFIDENTIAL

This material is the property of the NYU School of Medicine and Langone Medical Center. Do not disclose or use except as authorized in writing by the study sponsor
Interventional Template Version: 11 January 2019

1 Key Roles

[name], Principal Investigator
NYU Langone Health — Neurology
[name]
[contact]
[contact]

[name]
NYU Langone Health — Neurology
[name]
[contact]
[name]

[name]
Wake Forest School of Medicine
[name]
[contact]
[contact]

2 Introduction, Background Information and Scientific Rationale

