10.2 Statistical Hypotheses

We will test the hypotheses that there is an interaction between treatment (active vs. sham) and time on 1) distress (K10 & PANAS-NA) and 2) use (TLFB), with additional outcomes addressing mood/anxiety (BDI, STAI), detailed cannabis use (DFAQ-CU), craving (MCQ-17) and withdrawal (CWS).

If the interaction effect for an outcome is significant, we will conclude there is statistical evidence of overall treatment effect. If the spaghetti plots suggest trends (e.g., linear, quadratic, or piecewise changes) we will treat time as a continuous variable and fit repeated measures regression models along with group and its interaction with continuous time as independent variables.

In supplementary analyses, additional factors or covariates will be included in the models (along with their corresponding interactions with group and time) to examine the potential influence of gender, age, MS disability (PDDS), depressive symptoms (BDI), anxiety (STAI) and CUD severity (CUDIT-R) on responsiveness to active vs. sham treatment.

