10.5 Sample Size

Power analyses were conducted independently for Aim 1 and Aim 2, wherein estimated effect sizes came from 2 independent manuscripts that used tDCS to measure changes in distress (Aim1) and estimated changes in cannabis use (Aim 2). In the planned study subjects will be assessed at 5 time points with the Change from V1 being used as a dependent variable (4 pieces of data per dependent measure per participant).

There is an anticipated interclass correlation coefficient (ICC) of 0.8 for the within-subjects measures. The design effect which accounts for multiple correlated observations within each subject, is estimated to be 4.2 ($DE = [1 + (5-1) 0.8]$). In a clustered setting, the sample size is $N_{\text{effective}} = nm/DE$ where n is the number of subjects required when m replications within participants are performed after accounting for the design effect (DE). The estimated number of individuals needed to detect an effect in the active RS-tDCS group is 28 for Aim 1 and 15 for Aim 2 (1-sided alpha of 0.05 and power of 80%).

CONFIDENTIAL

This material is the property of the NYU School of Medicine and Langone Medical Center. Do not disclose or use except as authorized in writing by the study sponsor
Interventional Template Version: 11 January 2019

For this study, we will utilize a 2:1 randomization based on pragmatic considerations including timeline, cost, and the added value of over recruiting to the Active group in order to have a better assessment of safety and tolerability data. In corporation this information into the total planned recruitment size, we arrived at n=42(=50 * 4.2 / 5). (28 allocated to active, 14 allocated to sham). We anticipate enrolling 52 participants which includes 10% drop out rate.

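### The efficacy model in 10.4.2 groups the data by timepoint and names no participant term, so fitted as written its standard errors are wrong, too small for the arm effect and too large for the arm-by-time interaction

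*Combined protocol and SAP*

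**What the plan says.** Section 10.4.2 names linear mixed effects models, fitted by REML in Matlab's fitlme. The dependent measures "will be nested within timepoint (Visit 1, 5, 10, 15, 20), with active/sham as fixed effects", with the model "predicting change from V1 values following each 5 session RS-tDCS interval". Timepoint is the only grouping named and arm the only fixed effect. No section gives a participant random effect or a within-participant covariance.

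The Statistical Analysis row of the Protocol Summary has the same sentence ("The dependent measures will be nested within timepoint (Visit 1, 5, 10, 15, 20), with active/sham as fixed effects") under a different method: "Multivariate linear regression will be used to evaluate the outcome of each Aim".

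Section 10.5 takes the participant as the cluster: "The design effect which accounts for multiple correlated observations within each subject, is estimated to be 4.2", using an ICC of 0.8. It describes "Change from V1 being used as a dependent variable (4 pieces of data per dependent measure per participant", and assumes a one-sided alpha of 0.05 with 80% power.

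Section 10.2 sets the decision rule on the treatment-by-time interaction: "If the interaction effect for an outcome is significant, we will conclude there is statistical evidence of overall treatment effect". It also allows repeated measures regression with continuous time, but only if plots suggest a trend, and again without a participant term.

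Section 4.2.1 defines the primary endpoints as change between baseline and treatment-end.

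**The concern.** Four change scores from one person share that person's V1 value and general level, so they are correlated. A random effect for timepoint does not account for this. The sample size calculation discounts the data for within-person correlation and the stated model does not, so the two sections describe different analyses.

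A programmer who follows 10.4.2 would report the arm effect with too narrow an interval. Since 10.4.2 says that the trial is a pilot meant to supply effect sizes for a later grant, that overstated precision would carry into the next trial. The interaction test of 10.2, run with the same grouping, would err the other way and could miss a real effect.

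Three further mismatches sit in the same sentences. The named fixed effects include neither visit nor arm-by-visit, which the 10.2 hypothesis needs. Visit 1 is listed as a timepoint although its change from V1 is zero by definition, while 10.5 counts four values. The Protocol Summary and 10.4.2 give the method different names.

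**Working it through.** **The plan's own figure.** With five measures and ICC 0.8, DE = 1 + (5 − 1) × 0.8 = 4.2, and n = 50 × 4.2 / 5 = 42, split 28:14. This reproduces. Section 10.5 thus counts 42 × 5 / 4.2 = 50 effective observations.

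**Correlation of the change scores (assumed; 10.5 does not give it).** If the raw scores have compound symmetry with any ICC ρ and variance σ², each change has variance 2σ²(1 − ρ) and two changes have covariance σ²(1 − ρ), so they correlate 0.5. If instead the 0.8 applies to the changes themselves, they correlate 0.8. A third case is raw AR(1) with correlation 0.8.

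**Arm coefficient, participant ignored.** With four rows each, 42 × 4 = 168 rows are treated as independent given timepoint. The true standard error exceeds the reported one by √DE, where DE = 1 + 3r and r is the correlation of changes.

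- r = 0.5: DE = 2.5, √DE = 1.58, effective rows 168 / 2.5 = 67, interval too narrow by 1 − 1/1.58 = 37%. One-sided error 1 − Φ(1.645/1.58) = 0.149; two-sided 0.215.
- r = 0.8: DE = 3.4, √DE = 1.84, effective rows 168 / 3.4 = 49, interval too narrow by 46%. One-sided error 1 − Φ(1.645/1.84) = 0.186; two-sided 0.288.

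REML fits to simulated data with r = 0.8 gave a ratio of 1.83 between the participant-grouped and timepoint-grouped standard errors.

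**Interaction, participant ignored.** The person's level cancels from a within-person contrast, so with equal visit variances the true standard error is √(1 − r) times the reported one: 0.71 at r = 0.5 and 0.45 at r = 0.8. For a linear slope the one-sided error is 1 − Φ(1.645/0.71) = 0.010 and 1 − Φ(1.645/0.45) = 0.0001.

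**Treatment-end difference.** This is a comparison at one visit, so correlation between visits hardly matters. Unequal variances do. Under AR(1) 0.8 the change variances at the four visits are 0.40, 0.72, 0.98 and 1.18, with mean 0.82. A pooled variance understates the last one: √(1.18/0.82) = 1.20, and 1 − Φ(1.645/1.20) = 0.085.

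**Simulated rejection under the null at nominal 5%** (28:14, complete data, four change scores):

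| Test | Compound symmetry (r = 0.5) | Raw AR(1) 0.8 |
|---|---|---|
| Arm, participant ignored, one-sided / two-sided | 15.2% / 21.8% | 16.8% / 25.2% |
| Arm, on participant means, one-sided | 5.0% | 5.0% |
| Arm-by-visit F test, participant ignored | 0.2% | 0.2% |
| Arm-by-linear-time, participant ignored, one-sided | 1.1% | 2.4% |
| Session-20 difference, participant ignored, one-sided | 5.2% | 8.6% |
| Session-20 difference, participant random intercept, one-sided | 4.8% | 8.2% |
| Session-20 difference, unstructured, one-sided | 5.0% | 4.9% |

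At r = 0.8 the arm test rejects 18.7% one-sided and 29.2% two-sided. The one-sided 15% to 19% range is the same if the zero Visit 1 rows are kept, and at n=52 (split 35:17 assumed).

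**The case against.** **Participant grouping may have been meant.** The section names linear mixed effects models, 10.5 treats the participant as the cluster, and nesting within timepoint may only describe the data layout. This stands as a reason to doubt that anyone would code the sentence literally. It does not rescue the sentence, which names a grouping factor, and the wrong one for this purpose.

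**The decision rule is the interaction, not the arm coefficient.** This stands, and it limits the harm. A reader might infer that an ineffective device would be declared effective three to four times too often. The documents do not support that. Section 10.2 concludes on the interaction, for which the omission is conservative. The inflated rate applies only if the arm coefficient is taken as the deciding test.

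**Interval-specific estimates are planned.** Section 10.4.2 goes on to promise least-squares means effect sizes in four session intervals, with elapsed days as a covariate. So it would be too strong to say that 10.4.2 offers nothing by visit. That paragraph gives no participant term either, and the stated fixed effects would not produce those estimates.

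**It is a pilot, and the point estimate is sound.** With complete data and four post-V1 rows the arm estimate is not biased. But intervals around effect sizes are what a pilot hands on, and 10.2 still draws conclusions from significance.

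**Conclusion.** The model is wrong as written in 10.4.2 and the Protocol Summary, and it conflicts with the clustering assumed in 10.5. It should be fixed before analysis. If coded literally:

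- the arm coefficient has a standard error too small by a factor of about 1.6 to 1.8, with type I error of about 15% to 19% one-sided or 22% to 29% two-sided at nominal 5%;
- the 10.2 interaction has a standard error too large, with null rejection of about 0.2% for the F test and about 1% to 2.5% one-sided for a linear slope (lower still if changes correlate 0.8), so power is lost;
- the treatment-end difference is close to nominal under compound symmetry and about 8.5% under AR(1) 0.8, the excess coming from unequal visit variances.

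The sizes rest on complete data, a 28:14 split and the assumed correlations. For the arm coefficient the direction holds for any positive correlation of changes. If participant grouping was intended and is used, the arm and interaction errors do not arise and what remains is a text that fails to say so.

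**What to change.** In 10.4.2 and the Protocol Summary, replace the nesting sentence with an explicit model:

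- Linear mixed effects model, REML, with change from V1 at sessions 5, 10, 15 and 20 as the response. Visit 1 is not a response row.
- Fixed effects: arm, visit (categorical) and arm-by-visit.
- Participant as the grouping unit, with a within-participant covariance that allows unequal visit variances: unstructured where it converges, otherwise a participant random intercept. The fallback does not protect the session-20 contrast when variances differ (8.2% above), so report if it was used.
- The exact model formula, after checking that the named software can fit this covariance.

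Keep the interaction test of 10.2. Because the response is already a change from V1, arm-by-visit alone asks whether the arm difference varies over the four sessions; a steady difference sits in the arm term. Say whether the 10.2 interaction means arm-by-visit alone or both terms together. Report the session-20 arm difference from the same model, because 4.2.1 names treatment-end. State which of the two decides, and at what alpha and sidedness; that choice belongs to the investigators.

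In the Protocol Summary, change the method name from multivariate linear regression to linear mixed effects model.

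The cost is wording and code. Visit and arm-by-visit add 3 + 3 = 6 fixed-effect parameters, and an unstructured covariance for four visits has 10. No new data are needed, and n=42 stays because 10.5 already assumes within-subject clustering.
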